BIOFEE SOMATO

Neurovegetative decoupling in the visceral-brain axis and cognitive-emotional vulnerability in somatoform disorders: Interest of vagal biofeedback

BIOFEE-SOMATO

Monocentric study

N° CHU Promoter 38RC20.275

N° ID/RCB : 2020-A02155-34

Version N°1.1- Date: 10/11/2020

Principal Investigator	Pr [name] Hépato-Gastroenterology department, CHU Grenoble Alpes Email : [contact] Tel (direct) : [name] Pole : DIGIDUNE Fonction : Médecin
Promoter	CHU Grenoble Alpes, Délégation à la Recherche Clinique et à l'Innovation [name]

STUDY PROTOCOL & STATISTICAL ANALYSIS PLAN

I : Study protocol

The study requires 3 sessions (T1 / T2 / T3) with at least 24 days between each. The 3 sessions are identical in term of experimental design.

The first session (T1) will start by asking to the participants to answer to 8 self-reported questionnaires (STAI Y-A, PANAS, CES-D, PSS, CFS, VAS, SWLS and ICQ-18) aiming to evaluate the emotional state, the life satisfaction and the acceptance level of pathology.

It will be followed by an examination of the autonomic nervous system [ANS] functioning and the ANS - central nervous system [CNS] – enteric nervous system [ENS] electrophysiological coupling by using different electrophysiological tools (electrogastrogram [ECG], galvanic skin responses [GSR], photoplethysmography [PPG], breathing belt, electrogastrogram [EGG], electroencephalogram [EEG]). All the electrophysiological recordings will be synchronized and an acclimatization period will be respected. The recordings will be done seated in a quiet room. The physiological measures will ever be recorded at rest (30 minutes, eyes-closed), during a reactivity emotional task (reactivity period) and in the recovery period following the task (30 minutes, eyes-closed). Electrophysiological data will be collected by the acquisition systems BIOPAC® (MP 150, CEROM, France) and BioSemi®. The ECG data will be recorded using 3 single use and adhesive electrodes placed on the inner side of the right wrist, on the right shoulder and on the left side in accordance with the DII standard position (Einthoven). Physiological data recorded are related to the heart rate variability [HRV]. The breathing effects on the HRV will be controlled by means of the breathing rate recording using a breathing belt. The GSR data will be recorded using 2 skin sensors placed on the third phalanx of the forefinger and of the middle finger of the left hand. Physiological data recorded are related to the cholinergic sympathetic activity (tonic GSR / phasic GSR). The PPG data will be recorded using a finger sensor. Physiological data recorded are related to the adrenergic sympathetic tone and allowing a record of the blood pulse waves associated with the heart rate. The EGG data will be recorded using 6 single use and adhesive electrodes placed on the skin of the abdomen. Physiological data recorded are related to the gastric electrical activity. The EEG data will be recorded using a EEG headsets including 64 electrodes. The EEG is related to the brain activity generated by the neural functioning. The emotional reactivity task will be explained carefully.

The emotional reactivity computerized task was developed specifically for our protocol with OpenSesame® software. The task looks like a type of stroop task. Instructions are to identify as soon as possible the ink color of the word on the screen matches the meaning of the word, in doing as less as possible mistake. We ask to the participants to press a specific button on the keyboard in the case of the ink color of the word matches the meaning of the word and to press on another button on the keyboard if they don't. We developed the task in 3 similarly but not identical versions with the aim of randomly testing the 3 versions on each participant. Each version lasts 12 minutes and has some particularities such as the colors of the words. We generated 3 versions of the task in the aim to limit the classical habituation effect in participants. Each version is made of 6 blocs in 20 trials that is aiming at progressively increasing the stress level because of an increase of the mental load. Bloc 1¹ and bloc 2 are associated with a low stress, bloc 4 and bloc 5 are associated with a moderate stress and bloc 5 and bloc 6 are associated with a high stress. The increase of the mental load is permitted by slowly decreasing the word presentation time, by putting feed-back, instruction switches, time constraints and lastly, by the necessity to do a dual task.

STAI Y-A / PANAS / CES-D / PSS / CFS / SWLS / ICQ-18	ECG/EGG/EEG/ GSR/PPG/Emwave/ respiratory belt positioning	Resting period (30 minutes, seated, eyes closed)	Reactivity period (during the task, seated)	VAS	Recovery period (30 minutes, seated, eyes closed)
--	---	--	---	-----	---

3h30

The period (24 days) between the first session and the second session (T1-T2) will be considered as the control period. The larger BFB effects than the unspecific effects related to the spontaneous physiological and emotional variations will be verified through the control period. We will measure the parameters of interest before (T1) and at the end of the control period (T2). During the period, the participants will have to answer to online questionnaires (SSQ6, MAIA-2, STAI Y-B, Brief-Cope, BFI-N, CTQ) aiming to examine the psychological profile (social support, interceptive sensitivity, trait anxiety, style of coping, early life events).

The second session (T2), T1 + 24 days, will be similar of the first session. We will use the same questionnaires and will record the same electrophysiological parameters. At the end of the

[figure not shown]
¹ The bloc 1 will not be included in the final statistical analysis because is considered as a training bloc. This choice in accordance to the potential biases related to the increase of the sympathetic activity at the beginning of the task caused by a simple moving to action following the resting period.

second session, a short training session of the biofeedback [BFB] technique will be done and the software using for the biofeedback training will be supplied to each participant included in the experimental group to allowed to us to practice BFB by their self at home. The installation of the program and the explanations needed for using it, will be done during the second session (T2). The BFB software (Emwave Pro®) includes a photoplethysmography sensor that can be positioned on the earlobe. The participants will have to practice the biofeedback technique the next 24 days (3X5 min/day).

The period (24 days) between the second session and the third session (T2-T3) will be considered as the intervention period. At the end of the second session (T2), the participants will be separated into two inter-subject groups: an experimental group performing BFB technique (3X5 min per day) in the intervention period (T2-T3) and a control group not performing a specific exercise in the intervention period (T2-T3). The first 40 participants (20 IBS / 20 PNES) will be included into the experimental group (BFB training) whereas the last 10 participants (5 IBS / 5 PNES) will be included into the control group (no training). The participants won't be informed of the condition to which they belong. We will measure the parameters of interest before (T2) and at the end of the intervention period (T3). During the intervention period, all the participants will have to answer to online questionnaires (BVAQ-B, LES, DHS) aiming to examine the psychological profile (alexithymia, traumatic events).

The third session (T3), T2 + 24 days, will be similar of the two previous sessions. We will use the same questionnaires and will record the same electrophysiological parameters. Finally, a debriefing will be done at the end of the session for each participant. The session will be considered as the end of the study visit.

Concerning the online questionnaires: the package 1 is constituted by the SSQ6, the MAIA-2 and the STAI Y-B. The package 2 is constituted by the Brief-Cope, the BFI-N and the CTQ. The package 3 is constituted by the DHS. The package 4 is constituted by the BVAQ-B and the LE

II : Statistical analysis plan

Independent variables

Analysis A:

The participants will be separated into two inter-subject groups:

- An experimental group performing BFB technique in the intervention phase (T2-T3)
- A control group no performing an exercise in the intervention phase (T2-T3)

The participants won't be informed of the condition to which they belong.

Independent variables

- Measurement time (T1 / T2 / T3) intra-subject
- Group (experimental group / control group) inter-subject

Analysis B:

The participants will be separated into two inter-subject groups performing by a cluster analysis (HF or RMSSD) in the first session (T1):

- A dysfunctional neurovegetative profile (low vagal tone + low vagal flexibility) group
- A functional neurovegetative profile (high vagal tone + high vagal flexibility) group

The participants won't be informed about their neurovegetative profile. We will include all the participants.

Independent variable

- Neurovegetative profile (dysfunctional profile / functional profile) inter-subject

Analysis C:

The participants will be separated into two inter-subject groups performing by a cluster analysis (HF or RMSSD) in the first session (T1):

- A dysfunctional neurovegetative profile (low vagal tone + low vagal flexibility) group
- A functional neurovegetative profile (high vagal tone + high vagal flexibility) group

The participants won't be informed about their neurovegetative profile. We will include only the experimental group performing the BFB technique.

Independent variables

- Neurovegetative profile (dysfunctional profile / functional profile) inter-subject
- Measurement time (T2 / T3) intra-subject

Dependent variables

Physiological variables:

ECG –HRV:

- HF (0.15-0.40 Hz – high frequency) frequency-domain parameter
- LF (0.04-0.15 Hz – low frequency) frequency-domain parameter
- LF-0.1 Hertz (0.075-0.108Hz - spectral power of the low-frequency 0.1Hz band) frequency-domain parameter
- LF/HF (ratio of LF to HF power) frequency-domain parameter
- Total power (total power of the 0-0.40 Hertz band) frequency-domain parameter
- RMSSD (root mean square of successive RR interval differences) temporal-domain parameter
- SDNN (standard deviation of all NN intervals) temporal-domain parameter
- EDR (ECG-derived-respiration)

GSR (tonic GSR / phasic GSR):

- SCR frequency: number of the spontaneous galvanic skin responses by periods
- SCR amplitude: amplitude of the spontaneous galvanic skin responses by periods
- Integrated skin conductance responses [ISCR]: area of the galvanic skin responses identified on the signal

PPG:

- Pulsatility index variation (PI): Transit time flow

Breathing belt:

- Breathing rate by cycles per minute

EGG:

- Dominant power
- Total power [0-0.15 Hertz]
- Slow-waves frequency per minute

EEG:

- Spontaneous brain rhythms: spectral power of the 0-30 Hertz band

Physiological adaptation to the aversive situation (emotional reactivity task):

HRV, GSR and PPG differences will be calculated to measure the physiological changes causing by the task compared to the resting and the recovery periods. The differences will be calculated as follows:

- Physiological reactivity during the task compared to the resting period (Δ = reactivity HRV – resting HRV / Δ = reactivity GSR – resting GSR / Δ = reactivity PPG – resting PPG)
- Physiological recovery following the task (Δ = recovery HRV – reactivity HRV / Δ = recovery GSR – reactivity GSR / Δ = recovery PPG – reactivity PPG)

- Physiological recovery following the task compared to the resting period (Δ = recovery HRV – resting HRV / Δ = recovery GSR – resting GSR / Δ = recovery PPG – resting PPG)

Psychological variables:

- Alexithymia score (BVAQ-B)
- Neuroticism score (BFI-N)
- Trait anxiety score (STAI Y-B)
- Style of coping (Brief Cope)
- Positive affectivity score (PANAS)
- State anxiety score (STAI Y-A)
- Depressive symptoms score (CES-D)
- Perceived-stress level (PSS)
- Coping flexibility + metacoping scores (CFS + VAS)
- Acceptance score (ICQ-18)
- Social support score (SSQ6)
- Interceptive sensitivity score (MAIA-2)
- Life satisfaction score (SWLS)
- Negative impact scores (LES)
- Frequency, severity and intensity scores (DHS)
- Abuse scores (CTQ)

Statistical analyses

All statistical analyses will be performed using IBM SPSS Statistics®, R software® and JASP®. The alpha value for statistical significance will set at $p<0.05$.

Analyses of the scores collected will be done in several stages:

- Highlighting outlier participants to exclude from our statistical analysis.
- All the conditions for application of statistical tests will be verified.
- In the case of a failure to respect the conditions for parametric test application, we would make a data transformation to jointly improve normality and homogeneity residues. If the normality is failed and the homogeneity is respected, we would execute non-parametric tests.
- Analysis will be done on the subjects included. Analysis concerning the reactivity period (during the task) will be performed on the all blocs excepted the bloc 1².
- Main and secondary judgment criterions analysis will be performed by parametric tests or by non-parametric tests depending on the conditions for application:

• *Analyse A:*

- An ANOVA to repeated measurement with an intra factor (measurement time: T1 / T2 / T3) and an inter factor (group: experimental / control) on the physiological and psychological data collected.
- Student's test for independent samples will be performed on the psychological scores collected in the second session (T2) to account for the initial level of psychological states between the 2 groups.

² The bloc 1 will not be included in the final statistical analysis because is considered as a training bloc. This choice in accordance to the potential biases related to the increase of the sympathetic activity at the beginning of the task caused by a simple moving to action following the resting period.

- Contrasts will then be made by group on the scores in order to specify the effect of the condition on the physiological and psychological data.
- *Analyse B:*
 - K means non-hierarchical clustering will be performed with K = 2. To categorise participants depending on their resting neurovegetative profile (low vagal tone / high vagal tone) and on their dynamical neurovegetative profile (low vagal flexibility / high vagal flexibility), two K means non-hierarchical clustering will be performed with K = 2. One with HF or RMSSD and one with Δ HF or Δ RMSSD.
 - Student's test for independent samples (dysfunctional neurovegetative profile / functional neurovegetative profile) will be performed on the psychological vulnerability (trait scores) collected.
- *Analyse C:*
 - An ANOVA to repeated measurement with an intra factor (measurement time: T2 / T3) and an inter factor (neurovegetative profile: dysfunctional profile / functional profile) on the physiological and psychological data collected only into the experimental group performing the BFB technique.
- *Correlational analysis:*
 - Regressions or the Pearson correlations will be performed in order to measure the inter-signal correlation (ECG-EGG-EEG)
 - Regressions or the Pearson correlations will be performed in order to test our hypothesis about the HF/RMSSD related to the "low vagal tone" profile will be more correlated to Δ HF/RMSSD related to the "low vagal flexibility" profile than to Δ HF/RMSSD related to the "high vagal flexibility" profile. As the same as HF/RMSSD related to the "high vagal tone" profile will be more correlated to Δ HF/RMSSD related to the "high vagal flexibility" profile than to Δ HF/RMSSD related to the "low vagal flexibility" profile

Additional analyses

- We will control the age effect and the gender effect.
- Some additional statistical analyses will be exploratory: stability of the resting and the dynamical neurovegetative endophenotypes before the control period (T1) and at the end of the control period (T2).
- Correlation between the LF 0.1Hz and the clinical outcomes.
- To confirm the physiological effects of the BFB (BFB vs pseudo-BFB) on the flexibility of the electrophysiological coupling concerning the brain-visceral axis.

Sample

Power analysis (G * Power; Faul et al., 2007) was performed to determine a priori the sample size needed for this study. The power analysis, for an ANOVA (repeated measures, within-between factors), was performed for an effect size (η_p^2) of .12 with a power of .95 on the main judgment criterion (HRV – vagal tone HF) and reported a necessary sample of at least 22 participants (Kudo et al., 2014; Paul & Garg, 2012; Wells et al., 2012). We decided to include at least 25 IBS patients SII (20 test & 5 control) and 22 PNES patients (20 test & 5 control) in accordance with the possible inclusion rate and the duration of the study.

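### Stress-task version is in no planned model, so any difference between the three versions adds avoidable noise to the reactivity and recovery outcomes and possibly to the T1 flexibility profiles (minor)

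*Combined protocol and SAP*

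**What the plan says.** The description of the emotional reactivity task in Part I (Study protocol) says: "We developed the task in 3 similarly but not identical versions with the aim of randomly testing the 3 versions on each participant". The reason given is "We generated 3 versions of the task in the aim to limit the classical habituation effect in participants". On how the versions differ, it says only: "Each version lasts 12 minutes and has some particularities such as the colors of the words". With three sessions of the same design, I read this as one version per session in random order. The text gives no procedure for drawing the order, and no data on whether the versions are equally stressful.

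The task feeds a family of outcomes. Part II (Dependent variables) says: "HRV, GSR and PPG differences will be calculated to measure the physiological changes causing by the task compared to the resting and the recovery periods".

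Part II (Statistical analyses) gives the models:

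- Analysis A is "An ANOVA to repeated measurement with an intra factor (measurement time: T1 / T2 / T3) and an inter factor (group: experimental / control").
- Analysis C has measurement time (T2, T3) as its within-subject factor and an "inter factor (neurovegetative profile: dysfunctional profile / functional profile) on the physiological and psychological data collected only into the experimental group".
- Analysis B compares profiles formed at T1 by two K-means clusterings, one on HF or RMSSD and one on the change in HF or RMSSD.
- The only other adjustment, under Additional analyses, is: "We will control the age effect and the gender effect".

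Version and version order appear in none of these. On group sizes, Part I puts the first 40 participants in the biofeedback group, "whereas the last 10 participants (5 IBS / 5 PNES) will be included into the control group (no training").

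**The concern.** The versions are described as not identical, and every reactivity or recovery difference is measured against whichever version the participant met that day. If one version is more stressful, its effect varies from session to session within a participant. The time by group ANOVA has no term that can take this variation out, so it goes into the residual. With only 10 controls, the versions may also be unevenly spread at T2 or T3 in the one trial that is run.

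Precision on the reactivity and recovery contrasts is at stake, in a design where the control group already limits it. A second exposure is the T1 flexibility clustering. If the clustered change is task-based, each participant contributes one session and one version, and nothing averages out.

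**Working it through.** **The plan's own figure.** The plan gives no figure on version. Its one sample-size figure, 22 participants, reproduces for two groups and three sessions with correlation 0.5. With f² = 0.12/0.88 = 0.136, λ = f²·N·m/(1−ρ) = 0.136 × 22 × 3/0.5 = 18.0 on 2 and 40 df, which gives power 0.964; the computed minimum is 21, or 22 for two equal groups. That figure concerns vagal tone HF and does not depend on task version.

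**Inputs.** From the documents: 40 and 10 participants, three versions, three sessions, α = 0.05. Assumed, because the documents give no values: outcome SD 1, correlation between sessions 0.5, one version offset by d (0 to 0.8 SD), a true biofeedback effect of 0.8 SD at T3, and an independent random order for each participant.

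**Chance imbalance.** Two versions cannot both be used by 6 of 10 controls, so the probabilities add: 3 × P(Bin(10, 1/3) ≥ 6) = 3 × 0.0766 = 0.23. For one particular version, such as the offset one, the probability is 7.7%.

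**Noise added to the T3−T2 group contrast.**

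- The SD of a participant's change is √(2 × (1 − 0.5)) = 1, so the ordinary SE is √(1/40 + 1/10) = √0.125 = 0.354.
- Version effects (0, 0, d) have variance 2d²/9. Two draws without replacement from three differ with variance 3 × 2d²/9 = 2d²/3.
- The contrast therefore gains an error of mean 0 and SD √(0.125 × 2d²/3) = d/√12.
- For d = 0.5 this is 0.144, and the SE becomes √(0.125 + 0.0208) = 0.382, a rise of 8%.
- For d = 0.25 it is 0.072, a rise of 2%. For d = 0.8 it is 0.231, giving √(0.125 + 0.0533) = 0.422, a rise of 19%.

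**Type I error, by simulation of the planned time by group test.** With random order and no version term it stays at 0.044–0.056 across the offsets tried. The mean version-induced error is zero. With a version term it is 0.047–0.054.

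**Power for a 0.8 SD effect, random order.**

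| Version difference | As planned | With version term |
|---|---|---|
| None | 0.625 | 0.614 |
| One version offset 0.5 SD | about 0.55 | about 0.62 |
| One version offset 0.8 SD | about 0.47 | about 0.62 |
| Evenly spaced, extremes 0.5 SD apart | 0.58 | 0.63 |
| Evenly spaced, extremes 0.8 SD apart | 0.52 | 0.63 |

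**Balancing the orders without a version term.** In blocks of the six orders within group, at a 0.5 SD offset, the chance error in the contrast falls from SD 0.144 to 0.053. The version variance stays in the residual, however, so type I error falls to about 0.03 and power does not improve (0.556 against 0.554). With versions evenly spaced 0.8 SD apart, type I error falls to 0.021. The test becomes conservative and gains nothing.

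**Profile classification.** Take 50 participants, normally distributed changes and K-means with K = 2. A 0.5 SD offset in one version reclassifies about 9% of participants and makes those who drew that version about 19 percentage points more likely to fall in one cluster. For 0.25 SD the figures are 5% and 10 points. This applies only if the clustered change is the task-based one.

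**The case against.** The strongest reply is that randomisation already deals with this. If the order is random per participant, version is independent of session and group in expectation, and its variance is reflected in the residual against which the effect is tested. That stands. A reader might infer that version differences could be mistaken for biofeedback effects, but under the order the protocol describes the false-positive rate stays near 5%.

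A reader might also infer systematic confounding, because the controls are the last 10 enrolled and the drawing procedure is not given. That would need version order to drift with enrolment or differ between groups. If each group had its own fixed order, a 0.5 SD gap between the extreme versions could give 57% false positives. The documents describe random testing and nothing of that kind, so they do not support this reading. Nor do they show that the randomisation is unbalanced: a balanced random list is compatible with the wording.

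Three further replies have weight. All versions share length, number of blocs and stress progression, and the one named difference is word colour, so the true offset may be near zero. The 23% counts any of the three versions and should not be joined to a calculation in which only one is offset. The criterion used for sample size is vagal tone HF, and the resting recording precedes the task in each session, so resting HF is not affected by that session's version. These limit the size and scope of the point. They do not remove it, because the version term costs almost nothing if the versions are equivalent.

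**Conclusion.** The point holds as a minor loss of precision, confined to measures taken during or after the task and, conditionally, to the T1 flexibility profiles. Leaving version out neither biases the biofeedback contrast in expectation nor inflates type I error. It gives up about 7 points of power (0.55 against 0.62) if one version is offset by 0.5 SD, about 15 points (0.47 against 0.62) at 0.8 SD, and nothing if the versions are equivalent. These figures rest on the assumed offset, the correlation of 0.5, the 0.8 SD effect and truly random order. For Analyses B and C, the version drawn at T1 adds classification noise if a task-based change is clustered. Under random order that noise is unrelated to psychological traits, so it would tend to blur profile differences rather than create them.

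**What to change.** 1. In Analyses A and C, add task version (three levels) as a within-subject factor for every reactivity and recovery outcome. Version changes from session to session within a participant, so the model should be fitted with one row per session, for example as a linear mixed model. Resting measures need no change.
2. For Analyses B and C, state which change in HF or RMSSD is clustered, and tabulate T1 version by neurovegetative profile.
3. State how the version order is drawn. As support only, use a list of the six orders in permuted blocks within each group, spread over IBS and PNES. Adopt it only together with the version term, because balancing alone makes the planned test conservative.

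The cost is two degrees of freedom, about one point of power if the versions are equivalent, and a prepared order list. No extra visits, staff or participants are needed.

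### The protocol promises to control HRV for breathing, but no HRV analysis does so; with only one arm trained and no breathing instruction at rest, T3 resting HF may mix in-session use of the technique with change in vagal tone

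*Combined protocol and SAP*

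**What the plan says.** **Training.** Part I of the protocol places a short biofeedback session at the end of T2 and gives the software to the experimental group. Then "The participants will have to practice the biofeedback technique the next 24 days (3X5 min/day"). The comparator is "a control group not performing a specific exercise in the intervention period (T2-T3"), and its ten participants are labelled as having no training. "The third session (T3), T2 + 24 days, will be similar of the two previous sessions".

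**Recording conditions.** Recordings are made seated in a quiet room after acclimatisation. The session table gives "Resting period (30 minutes, seated, eyes closed"), and the recovery period is described in the same way. Neither entry mentions spontaneous breathing or refraining from exercises.

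**Breathing.** Part I states: "The breathing effects on the HRV will be controlled by means of the breathing rate recording using a breathing belt". In the SAP, under Dependent variables, the belt contributes "Breathing rate by cycles per minute", and ECG-derived respiration is listed under the ECG–HRV heading. For the reactivity and recovery scores, "HRV, GSR and PPG differences will be calculated to measure the physiological changes causing by the task"; the belt is not named there.

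**Models.** Under Statistical analyses, Analysis A is a time (T1/T2/T3) by group ANOVA. Analysis C is a time (T2/T3) by neurovegetative profile ANOVA in the trained group only. Under Additional analyses the named control factors are age and gender. The Sample section gives the main criterion as HRV, vagal tone HF.

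**The concern.** At T1 and T2 nobody has been taught the technique when the resting recording is made, because training comes at the end of T2. At T3 one arm has a practised skill and the other does not. Trained participants then sit quietly with eyes closed for 30 minutes, with no stated instruction about breathing or exercises. Some may use the skill, deliberately or from habit.

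The main criterion is meant to describe resting vagal tone. If the technique is in use during the recording, T3 HF reflects what the participant is doing at that moment as well as any lasting change. The T1–T2 control period cannot reveal this, because it ends before training. Analysis A compares people who could use the skill with people who could not. The time effect in Analysis C has no untrained comparator. The planned correlation of LF 0.1 Hz with clinical outcomes is exposed in the same way.

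The belt control promised in Part I is the natural safeguard, but the SAP does not carry it into any HRV analysis.

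**Working it through.** **1. The plan's own figure.** The Sample section reports at least 22 participants for partial eta squared .12 and power .95. With f² = .12/.88 = 0.136, two groups, three times, alpha .05, and assumed correlation 0.5 and sphericity (neither is stated), the noncentrality is λ = f² × N × 3/(1 − 0.5). At N = 22, λ = 18.0 with 2 and 40 degrees of freedom, and power is 0.964. The smallest N reaching .95 is 21, or 22 with equal groups. The figure reproduces and is not in dispute.

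**2. Promise against analysis.**

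| Element | Part I | SAP |
|---|---|---|
| Breathing effect on HRV | To be controlled with the belt | No term, stratum or exclusion in any HRV model |
| Belt rate | Recorded | Separate dependent variable |
| Named controls | – | Age, gender |
| Rule linking breathing result to HF result | – | None |

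Belt rate falls within the physiological data that Analyses A and C cover, so a group difference in breathing can be tested. That is not the same as controlling its effect on HRV.

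**3. What the SAP's bands imply.** The inputs are the limits under Dependent variables, multiplied by 60.

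- HF, 0.15–0.40 Hz: 9.0 to 24.0 cycles/min.
- "LF-0.1 Hertz (0.075-0.108Hz"): 0.075 × 60 = 4.5 to 0.108 × 60 = 6.48 cycles/min.

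Respiratory power therefore leaves HF below 9 breaths/min, and enters the 0.1 Hz band at about 4.5–6.5/min. Whether trained participants breathe at such rates is an assumption.

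**4. Can the bias be sized?** Not from the documents: they give no pace, no rate of in-session use and no HF variance. A what-if calculation shows only how the test responds. Take T2–T3 change scores, 40 against 10, with no true resting change. A share q of the trained arm shifts by s standard deviations of change, so the mean difference is q × s. For scale, partial eta squared .12 corresponds to √(0.136 × 48) × √(1/40 + 1/10) = 0.90 SD. The simulated chance of p < 0.05 (two-sided t test, nominal 0.05) is about:

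| s | q = 25% | q = 50% |
|---|---|---|
| 0.5 | 0.06 | 0.10 |
| 1 | 0.09 | 0.23 |
| 2 | 0.15 | 0.54 |

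Every s and q here is assumed. The range runs from negligible to serious and is not evidence that bias will occur. Where a true change exists, a shift in the opposite direction would hide it.

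**5. Which belt summary would help.** The SAP does not say over what interval breathing rate is summarised. As an assumed example, 25 minutes at 15/min and 5 minutes at 6/min give a mean of (25 × 15 + 5 × 6)/30 = 13.5/min, which looks ordinary. One-minute rates would put at least 4 of those 5 minutes below 9/min. Time below 9/min is therefore a better summary than the period mean.

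**The case against.** **Breathing is analysed.** A reader might infer that the SAP ignores the belt. It does not: belt rate is an outcome in Analyses A and C, and a difference at T3 would be visible. This narrows the point to two gaps: no HRV analysis uses the belt, and no rule says how a breathing result qualifies HF.

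**The mechanism is not documented.** No text says that the technique slows breathing or that anyone would use it while being recorded. That is right, and so no direction can be given. A reader might infer that HF will be inflated, or depressed; the documents support neither. A missing script in a short protocol also does not prove that staff give none.

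**Practice running into T3.** Because practice lasts 24 days and T3 is at T2 + 24 days, a reader might infer that practice continues on the T3 day. That depends on how days are counted. The opening of Part I requires at least 24 days between sessions, so practice may end before T3. Practising earlier that day would not be in-session use in any case.

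**Analysis C.** A reader might infer that its time by profile interaction is biased. Both profiles are trained, so this would need use to differ by profile, and nothing in the documents suggests that it does. Only the time effect lacks an untrained comparator.

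**Skill use may be the benefit.** During recovery from a stressor, using the technique may be what the training is for. Forbidding it there would change what is estimated. This objection stands, and the fix respects it.

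**Conclusion.** The point holds in limited form. Part I states a control for breathing that no HRV analysis in the SAP delivers. Together with training in one arm only and an uninstructed resting period, this means that T3 resting HF in Analysis A, and the T2–T3 time effect in Analysis C, may not separate in-session use from change in resting vagal tone.

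The size and direction of any bias are unknown and cannot be set against the planned effect. The band limits are arithmetic from the SAP; slow breathing and in-session use are assumptions. The sample size is not affected. This is worth considering rather than critical, with medium confidence: the remedy is nearly free and concerns the main criterion, and unrecorded in-session use cannot be fully reconstructed later.

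**What to change.** 1. **Resting instruction.** At T1, T2 and T3, give every participant the same neutral sentence before the resting recording: sit quietly, breathe spontaneously, do no exercise. Do not mention a learned technique, because participants are not told their condition. Leave recovery uninstructed, or state explicitly whether skill use there is part of the effect being measured.
2. **Debriefing.** At the existing T3 debriefing, ask about use of any technique during the recordings and about the time of last practice.
3. **Supportive analysis, pre-specified.** By group and session, report breathing rate and the proportion of rest and recovery time below 9 breaths/min, from breath-by-breath or one-minute belt rates. Repeat the T2–T3 resting HF contrast without those segments, and report how much recording time is dropped in each group. Label it as conditioning on behaviour after allocation. Slower spontaneous breathing may itself be a training effect, and use of the technique at or above 9/min would be picked up only at the debriefing.

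The main ANOVA stays as planned. Breathing rate should not simply be added to it as a covariate: it is measured after training, and adjustment could remove part of a real effect.

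The cost is one scripted sentence, two debriefing questions and a small analysis of data already being recorded.
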